#### 10.4 Risk-Benefit Rationale

The main benefit of this study is that subjects may experience improved glucose control. Since Lyumjev insulin has not been previously studied with the MiniMed 780G system in all age groups, there is a theoretical risk that the MiniMed 780G pump's closed loop algorithm may not maintain the same level of glucose control achieved with other insulins although modeling has indicated that use of Lyumjev Insulin will not result in any clinically significant change in clinical outcomes. Additionally, risk related to the

D00409632 Version E Page 80 of 106

pump delivering too much or not enough insulin are further minimized through a variety of safety checks that are an integral part of the MiniMed 780G closed loop algorithm.

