#### 11.3 Recording of Adverse Events

The investigator or designee will record ALL AEs while the subject is enrolled in the clinical study. Each AE needs to be assessed for its device or procedure relatedness. A device related AE is associated

with the use of the study devices (e.g., infection of sensor site or infusion set occlusion resulting in DKA). A procedure related AE is associated with testing related to the study procedures specified in the CIP (e.g., needle (blood draw) insertion pain).

Examples of device or procedure related AEs include:

- *Device* related (ADE): insertion site infection
- Serious adverse *device effect*: cellulitis at device insertion site requiring hospitalization
- *Procedure* related AE: bruising at needle (blood draw) insertion site

Subjects participating in the study have diabetes and are expected to experience hypoglycemia and or hyperglycemia. These normal events are not expected to be reported to sponsor as this is not considered an untoward event, but rather an expected occurrence. Any glycemic excursion that meets the protocol definition of severe hypoglycemia, severe hyperglycemia or DKA is considered an untoward event and a worsening from the subject's baseline and would be reported to sponsor on an AE eCRF.

Baseline medical conditions should only be reported to sponsor on an AE eCRF if there is a worsening from the subject's baseline. For example, a subject previously diagnosed with asthma is hospitalized for severe asthma attack would be a reportable event.

D00409632 Version E Page 83 of 106

Adverse events will be documented in the subject source file and reported to sponsor on an eCRF. The investigational center is responsible for documentation of AEs including obtaining source documents related to the event, such as emergency medical technician/paramedic reports, hospital records (admission summary; lab results, test results, discharge summary) or device uploads to support the event. Source documents will be reviewed to determine if additional AEs have occurred and require reporting.

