#### 11.6 Causality Assessment

An AE is not automatically related to the study device or procedure simply because the subject is wearing the device and participating in the study. The event should be reviewed to determine if the device or study procedure could have possibly caused the event and therefore is related to the study device or procedure.

[figure not shown]
Causality assessment is the determination of the relationship between an AE and the device being studied. It is expected that the investigational center will review all elements surrounding the AE to properly assess the causality of the event to the study device or to a study procedure. This review would include the subjects' description of the event, study device uploads and medical records (if applicable) from the treating facility. These records will be made available to sponsor. Investigators should classify the relationship between the AE and the study device or study procedures using one of the four possible causality categories listed below:

- **Not related:** relationship to the device, comparator, or procedures can be excluded when:
  - o the event has no temporal relationship with the use of the investigational device or the procedures related to the application of the investigational device;
  - o the event does not follow a known response pattern to the medical device (if the response pattern is previously known) and is biologically implausible;
  - the discontinuation of medical device application or the reduction of the level of activation/exposure - when clinically feasible - and reintroduction of its use (or increase of the level of activation/exposure), do not impact on the event;
  - the event involves a body-site or an organ not expected to be affected by the device or procedure;
  - o the event can be attributed to another cause (e.g., an underlying or concurrent illness/ clinical condition, an effect of another device, drug, treatment or other risk factors);
  - the event does not depend on a false result given by the investigational device used for diagnosis, when applicable;

In order to establish the non-relatedness, not all the criteria listed above might be met at the same time, depending on the type of device/procedures and the event.

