- **Possible:** the relationship with the use of the investigational device, comparator, or the relationship with procedures, is weak but cannot be ruled out completely. Alternative causes are also possible (e.g., an underlying or concurrent illness/clinical condition or/and an effect of another device, drug or treatment). Cases where relatedness cannot be assessed, or no information has been obtained should also be classified as possible.
- **Probable**: the relationship with the use of the investigational device, comparator, or the relationship with procedures, seems relevant and/or the event cannot reasonably be explained by another cause.
- **Causal relationship:** the event is associated with the investigational device, comparator, or with procedures beyond reasonable doubt when:
  - o the event is a known side effect of the product category the device belongs to or of similar devices and procedures;
  - the event has a temporal relationship with investigational device use/application or procedures;
  - the event involves a body-site or organ that
    - the investigational device or procedures are applied to;
    - the investigational device or procedures have an effect on;
  - o the event follows a known response pattern to the medical device (if the response pattern is previously known);
  - the discontinuation of medical device application (or reduction of the level of activation/exposure) and reintroduction of its use (or increase of the level of activation/exposure), impact on the event (when clinically feasible);

D00409632 Version E Page 85 of 106

- o ther possible causes (e.g., an underlying or concurrent illness/clinical condition or/and an effect of another device, drug or treatment) have been adequately ruled out;
- o harm to the subject is due to error in use;
- o the event depends on a false result given by the investigational device used for diagnosis, when applicable:

In order to establish the relatedness, not all the criteria listed above might be met at the same time, depending on the type of device/procedures and the event.

Example: A severe hyperglycemia AE with the following event description would have the following causality assessment for device relatedness:		
Improved glucose without an infusion set/site change	Not related	
Changed infusion set with glucose improvement	Possible	
Infusion set fell out, bent cannula, occlusion alarm	Causal relationship	

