- 1. Was the severe hypoglycemia or DKA related to the AHCL algorithm, or was it related to a known insulin pump risk? For example, a question that may be considered in DKA would be whether the event was related to an infusion set issue or caused by the AHCL algorithm.
- 2. Another important consideration would be if the severe hypoglycemia, severe hyperglycemia or DKA event was related to a device malfunction versus patient non-compliance. For example, if a software anomaly leading to an under-delivery of insulin is discovered versus the subject repeatedly ignoring alarms prompting the subject to take action.
- 3. Severe hypoglycemia, severe hyperglycemia or DKA caused directly by an infusion set issue when the study pump is functioning as intended would likely result in acceptance to proceed with the study versus severe hypoglycemia or DKA that are directly caused by the AHCL algorithm or a device malfunction might stop study enrollment or entire study altogether.
- 4. It should be noted that the final determination of causality related to 780G system that is made by the CEC may include additional factors which the members consider to be clinically relevant and important.

[figure not shown]

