#### The DMC will perform 4 main functions:

**First:** DMC will track and trend the overall safety of the study.

D00409632 Version E Page 87 of 106

Event rate, defined as number of events per 100 patient years, will be reviewed by the DMC with respect to the following:

- Event rate of all SAEs
- Event rate of severe hypoglycemia
- Event rate of severe hyperglycemia
- Event rate of DKA
- Event rate of device related AEs

Second: Based on their meetings, DMC will recommend a decision to the sponsor regarding the followina:

- Whether or not enrollment should be halted.
- Whether or not the entire study will need to be stopped including for those subjects who have received study devices already.

Note: If it is decided to withdraw subjects from participation in the study or if the study is stopped, subjects will be followed-up in accordance with standard practice by their own providers.

**Third:** During the study, the following steps will be taken for:

- Unanticipated adverse device effects (UADE)
- Device related DKA
- Device related severe hypoglycemia

DMC is to meet within 10 days from the time that the CEC adjudicates an event as one of the above. If possible, the investigator should be available to answer questions by DMC.

Based on their meetings, DMC will recommend a decision to the sponsor regarding the following:

- Whether or not enrollment should be halted.
- Whether or not the entire study will need to be stopped including for those subjects who have received study devices already.

Note: If it is decided to withdraw subjects from participation in the study or if the study is stopped, subjects will be followed-up in accordance with standard practice by their own providers.

Fourth: The DMC will review Safety data and provide a recommendation to the sponsor regarding staged enrollment of pediatric subjects:

The DMC will provide a recommendation to proceed with the following staged enrollment:

Enrollment of pediatric subjects 7-17 years of age into the study may not proceed until N=10 subjects 18 years of age or older have completed 30 days of the study period and the Data Monitoring Committee (DMC) has determined it is safe for subjects 7-17 years of age to be enrolled in the study.

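### No adverse event is assessed or tabulated for its relationship to Lyumjev, so one attributed solely to the insulin can be coded Not related; the worked causality example has a separate fault

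*Protocol*

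**What the plan says.** Protocol Section 3.2 sets the purpose as evaluating Lyumjev in the 780G system. The risk table in Section 10.1 gives Lyumjev its own list of risks, among them hypersensitivity, infusion site reaction and lipodystrophy. Section 10.4 adds a theoretical risk that the "closed loop algorithm may not maintain the same level of glucose control achieved with other insulins".

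The causality rules do not follow that purpose:

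- Section 11.3: "Each AE needs to be assessed for its device or procedure relatedness".
- Section 11.6: "Investigators should classify the relationship between the AE and the study device or study procedures using one of the four possible causality categories".
- Section 11.6, grounds for *Not related*: another cause, including "an effect of another device, drug, treatment or other risk factors".
- Section 11.6, *Possible*: "Alternative causes are also possible (e.g., an underlying or concurrent illness/clinical condition or/and an effect of another device, drug or treatment". This category takes weak links that cannot be ruled out and cases that cannot be assessed.
- Section 11.6, worked example for severe hyperglycemia: "Improved glucose without an infusion set/site change" is assigned *Not related*.

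Section 12.1 asks the Clinical Events Committee (CEC): "Was the severe hypoglycemia or DKA related to the AHCL algorithm, or was it related to a known insulin pump risk". Among the five rates that Section 12.2 names for the Data Monitoring Committee (DMC), the only one that depends on causality is the "Event rate of device related AEs". SAP Sections 7.9.6 and 7.10 list serious events, device effects (SADE, UADE), severe hypoglycemia, severe hyperglycemia and DKA. Neither lists events related to the insulin.

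**The concern.** The study is single-arm, so much of the work of separating an insulin effect from an infusion set, sensor or algorithm effect falls on recorded attribution. The attribution that matters most for the stated purpose is never requested. Device relatedness also controls several later steps: the ADE, SADE and UADE classes, the anticipated/unanticipated assessment in Section 11.7, the DMC's one causality-based rate, and the expedited review of DKA and severe hypoglycemia. An event placed outside device relatedness because the insulin caused it passes none of these gates. A low count of related events in a labeling submission could then partly reflect how events were coded.

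The worked example raises a second, independent worry. It settles device relatedness by whether the infusion set was changed, although the device under study also includes the pump, its algorithm and the sensor.

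**Working it through.** No arithmetic on rates, power or margins applies. The check sets the definitions side by side and follows event types through them.

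**Is there an axis that covers Lyumjev?** Section 11.2 takes device to mean any device used in the study, including marketed components. Section 11.3 ties procedure-related events to testing required by the protocol. Table 1 in Section 6.2 lists Lyumjev separately as an approved drug, and Section 6.4.1 places it among non-investigational products. Neither axis covers it.

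**Does *Possible* count as related?** Section 11.6 opens by treating an event the device could possibly have caused as related, so it does.

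**Where does each type of event go?**

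| Event | Code available | Still reaches | Misses |
|---|---|---|---|
| Non-serious, attributed solely to Lyumjev, device excluded (e.g. systemic hypersensitivity) | *Not related* | Adverse event record; the DMC's general safety remit | The only named DMC rate it could enter; the Section 11.7 step |
| The same, serious | *Not related* | CEC review; all-SAE rate; SAP summary of SAEs | Device-related rate; SADE; Section 11.7 step |
| DKA or severe hypoglycemia attributed solely to the insulin | *Not related* | Rapid notification; CEC review; its own DMC rate and SAP summary | Device-related rate; expedited CEC and DMC review |
| Lyumjev suspected, device link cannot be ruled out | *Possible* | All device-related routes for that event type | Any record that the insulin was suspected |
| Severe hyperglycemia improving without a set change | *Not related*, by the example | CEC review; its own DMC rate and SAP summary | Device-related count, unless the CEC reclassifies it |

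**What does the expedited route offer?** The CEC has 10 days from sponsor notification and the DMC meets within 10 days of adjudication, so at most 10 + 10 = 20 days. Routine DMC meetings are about 90 days apart, with ad hoc meetings allowed.

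**Is the worked example consistent with its surroundings?** The closed-loop part of the Section 10.1 risk table lists sensor under-reading, missed transmissions and moving into or out of SmartGuard as causes of hyperglycemia. Any of these could resolve without touching the infusion set. Improvement without a set change is evidence against a set failure and says nothing about the pump, sensor or algorithm. Under the general rule in the same section, an event with such a cause not ruled out belongs in *Possible*. The example assigns *Not related*, so the two must be reconciled.

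**The case against.** A reader might infer that every event attributed to the drug must be coded *Not related*, and that harm from Lyumjev therefore disappears. The documents do not support that:

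- Section 11.6 says the relationship can be excluded when the criteria apply; it does not require exclusion. *Possible* expressly tolerates a drug as an alternative cause. No passage says that Lyumjev delivered by the study pump is another drug; that reading is natural but inferred.
- Infusion site reactions rarely allow the device to be excluded. Pain, redness and rash are listed infusion set risks, and involvement of a site where the device is applied is a criterion for relatedness.
- Lyumjev reactions are also captured without any causality judgment: emails in weeks without a visit, visit questions with a dedicated form, mandatory reporting of moderate or severe site reactions, and withdrawal after two or more reportable ones.
- Section 9.9 does not limit stopping to device-related events. The DMC can meet ad hoc and tracks overall safety.

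It would also go too far to say that algorithm-caused events are sent to *Not related*. The CEC is asked directly about the algorithm, may examine pump and sensor data, and its adjudication is the one analyzed. Severe hyperglycemia is not itself an expedited trigger, so the example does not cost these events that review. The Section 11.7 loss is also small for risks already named in the protocol, since they would be classed as anticipated.

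Two further defenses carry less weight. The SAP reports safety separately for Visits 2 to 7 and from Visit 7 onward, but Lyumjev and SmartGuard with Auto Correction start together at Visit 7, so that comparison cannot separate insulin from algorithm. The study is a device investigation using device definitions and an approved insulin, which explains the missing axis; the stated purpose still asks about the insulin.

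**Conclusion.** The concern holds in limited form. No relationship to Lyumjev is collected or tabulated, and an event attributed solely to the insulin can be coded *Not related*. It then misses the device-related rate, the anticipated/unanticipated step and, for DKA and severe hypoglycemia, the expedited triggers. The *Possible* category does not repair this, because it records a weak device link and leaves the suspected insulin link unrecorded.

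The clearest loss is for non-serious events outside the named glycemic categories, which have no other named DMC rate. Serious events, severe hypoglycemia, DKA and severe hyperglycemia remain visible to both committees. The documents give no frequency for insulin-attributed events, so the number affected is unknown.

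The worked example is a separate fault. It can understate the device-related count where the CEC follows it. The conclusion rests on two assumptions: that sites read Lyumjev as another drug in Section 11.6, and that the event form carries no insulin item beyond what the protocol describes.

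**What to change.** 1. Add an item to the adverse event form, and to Sections 11.3 and 11.6, for relationship to study insulin (Lyumjev), using the same four categories. State in Section 11.6 that Lyumjev is not another drug for the purpose of the *Not related* ground.
2. Add to SAP Sections 7.9.6 and 7.10 a summary of insulin-related events that includes moderate and severe infusion site reactions, and report the same rate to the DMC. State in Sections 12.1 and 12.2 how DKA and severe hypoglycemia attributed to the insulin enter expedited review.
3. Reconcile the worked example with the *Possible* definition. Improvement without a set change should not by itself justify *Not related*; pump, sensor and algorithm data should be assessed under the general criteria.

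The cost is one form field, one table, and edits to the protocol and committee procedures. Related-event counts will rise somewhat, and a few more events will go to expedited review.

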Risks with Fingersticks and Blood Draws	Prevention and Mitigation
Risks with frequent fingerstick testing and blood draws may include:  • Potential risks associated with frequent meter testing of BG and blood ketones include discomfort and ecchymosis at tips of fingers  • Potential risks associated with fingerstick testing include discomfort and bruising  • Potential risks associated with drawing blood include discomfort, bruising and hematoma	
 
Prevention and mitigation include:
 
Follow the provided user guides for use of the study meter with fingerstick testing.
 
Train on the proper use of the study meter and fingerstick testing.
 
Blood draws will be performed by a trained healthcare professional
 

Risk with Closed Loop Therapy	Prevention and Mitigation
Risks with Closed Loop may include:	Prevention and mitigation include:  • Follow the provided user guides for insulin pump management.

D00409632 Version E Page 78 of 106

- Hypoglycemia
- Severe hypoglycemia
- Hyperglycemia
- Diabetic ketoacidosis
- User entry error
  - Patient administering boluses by entering false carb doses leading to hypoglycemia or hyperglycemia
  - Patient entering false glucose values for any reason leading to hypoglycemia and hyperglycemia
  - Patient entering false BG values for calibration leading to hypoglycemia or hyperglycemia
- Sensor failure resulting from patient failure to calibrate leading to hypoglycemia or hyperglycemia
- Sensor over-reading resulting in hypoglycemia
- Sensor under-reading resulting in hyperglycemia
- Sensor missed transmission, or any other fault resulting in no SG value, leading to hyperglycemia or hypoglycemia
- Voluntary insulin delivery (with the pump or with a syringe) immediately prior to entering SmartGuard may result in severe hypoglycemia despite shutting down insulin delivery by the algorithm
- Hypoglycemia related to patient taking insulin via injection while in Closed Loop (SmartGuard)
- Hypoglycemia or hyperglycemia related to entering or exiting Closed Loop (SmartGuard)
- Insulin over-delivery due to potential interference from acetaminophen
   Cyber security hacking into pump

- Train prior to study device use on appropriate device use and diabetes management principles and instruct to call investigator with problems.
- Instruct to check their meter glucose if their high or low symptoms do not match their sensor alerts or SG readings in order to make diabetes treatment decisions.

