#### 11.2 Definitions and Classification of Adverse Events

Medtronic uses the definitions provided in ISO 14155:2020 and 21 CFR 812 for AE definitions. Where the definition indicates "device", it refers to any device used in the study. This might be the device under investigation, or any market released component of the system.

Severe Hypoglycemia is an event requiring assistance of another person due to altered consciousness to actively administer carbohydrate, glucagon, or other resuscitative actions.

This means that the subject was impaired cognitively to the point that he/she was unable to treat himself or herself, was unable to verbalize his or her needs, and was incoherent, disoriented and/or combative.

These episodes may be associated with sufficient neuroglycopenia to induce seizure or coma. Plasma glucose measurements may not be available during such an event, but neurological recovery attributable to the restoration of plasma glucose to normal is considered sufficient evidence that the event was induced by a low plasma glucose concentration.

**Severe Hyperglycemia** is defined as hyperglycemia (BG greater than [>] 300 mg/dL or 16.7 mmol/L) with BG ketones greater than (>) 1.5 mmol/L, and/or accompanied by symptoms of nausea, vomiting or abdominal pain.

The meter and ketone test strips are supplied for the evaluation of ketone monitoring. Only blood ketones will be recognized (not urine ketones) for assisting in diagnosis of severe hyperglycemia. The

monitors/test strips are quality controlled prior to dispensing to subjects. Blood ketones provide contemporaneous understanding of ketone levels associated with elevations in glucose.

**Diabetic Ketoacidosis/DKA diagnostic criteria**: BG greater than (>) 250 mg/dL or greater than (>) 13.9 mmol/L, arterial pH less than (<) 7.3, bicarbonate less than (<) 15 mEq/L, moderate ketonuria or ketonemia and requiring treatment within a health care facility.

Hyperglycemic events will be recorded as DKA if the event includes the presence of all of the following:

- Arterial blood pH less than (<) 7.30 or serum bicarbonate less than (<) 15 mEq/L
- Blood glucose greater than (>) 250 mg/dL or greater than (>) 13.9 mmol/L
- Serum ketones or large/moderate urine ketones
- Symptoms such as polyuria, polydipsia, nausea, or vomiting
- Treatment provided in a health care facility

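### Read literally, the worked example in Protocol Section 11.6 leads sites to code severe hyperglycemia as not device related from infusion-set status alone, without excluding a sensor, pump or SmartGuard contribution

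*Protocol*

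**What the plan says.** The example in Protocol Section 11.6 is introduced in directive terms: "A severe hyperglycemia AE with the following event description would have the following causality assessment for device relatedness". It has three rows:

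- The first row, "Improved glucose without an infusion set/site change", is coded *Not related*.
- The second row, "Changed infusion set with glucose improvement", is coded *Possible*.
- The third row, "Infusion set fell out, bent cannula, occlusion alarm", is coded *Causal relationship*.

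No row mentions the sensor, transmitter, pump or algorithm.

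Other parts of the protocol bear on the same coding decision:

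- Section 11.2 says of the word device that "it refers to any device used in the study".
- Section 10.1 lists, under closed-loop risks, "Sensor under-reading resulting in hyperglycemia". It also lists lost sensor transmissions, moving into or out of SmartGuard, and SmartGuard's use of sensor values to calculate boluses.
- Section 11.6 reserves *Not related* for cases where a relationship can be excluded. It expects the site to consider the whole event, uploads included. For *Possible* it adds: "Cases where relatedness cannot be assessed, or no information has been obtained should also be classified as possible".
- Section 12.2 gives the DMC, among other rates, "Event rate of device related AEs".

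**The concern.** The example answers a question about all study devices with information about one of them. A site that follows it as written would code *Not related* for an event driven by a sensor error, a delivery fault or a SmartGuard exit, provided glucose came down without a set change.

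The gap falls on the products under investigation. Table 1 in Section 6.2 classes the pump, sensor and transmitter as investigational and the infusion set as non-investigational. Section 10.4 names, as a theoretical risk, that the closed-loop algorithm may not hold the same glucose control with Lyumjev, although modelling predicted no clinically significant change. An example that recognises set faults and says nothing about the closed loop could thin out the reports that bear on that risk.

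Three things depend on relatedness: device-effect coding (ADE and SADE), the Section 11.7 judgement of anticipated or unanticipated, which is made only for events held to be device related, and the DMC's device-related rate.

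**Working it through.** No calculation applies to a coding rule, so the check sets the texts side by side.

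1. **What the example uses.** All three rows are defined by what happened to the infusion set. Two events with the same set history receive the same code whatever the sensor, pump or algorithm did.

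2. **What it is meant to decide.** Its lead-in asks about device relatedness without limiting this to the set, and Section 11.2 makes device cover every study device. The input is narrower than the question.

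3. **Whether row 1 follows from the *Not related* criteria.** Section 11.6 lists grounds for exclusion and allows that not all need be met together. The nearest is the criterion on withdrawing and reintroducing the device: recovery with the same set in place is evidence against the set. It is no evidence about the sensor, pump or SmartGuard. Another ground is that the event did not depend on a false device result, where that applies; the row does not ask about this, and the reverse appears under *Causal relationship*.

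4. **A test case.** Suppose the sensor under-reads, the system delivers too little insulin, and the event meets the severe hyperglycemia definition in Section 11.2. Glucose then recovers and the set is never touched.
   - By row 1: *Not related*.
   - By the definitions: the timing fits, the mechanism is listed in Section 10.1, and the relationship cannot be excluded. The code is at least *Possible*, and the false-result criterion may point higher.

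   The two parts of Section 11.6 give different codes for the same event.

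5. **The unknown case.** If no upload is available, the section's default is *Possible*. Row 1 still gives *Not related*.

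6. **What happens to the code afterwards.**
   - Section 12.1 puts severe hyperglycemia on the CEC review list whatever the site coded. If the investigator and CEC still disagree, the CEC's call is analysed.
   - The 10-day CEC review covers unanticipated device effects, device-related ketoacidosis and device-related severe hypoglycemia. Severe hyperglycemia as such is not on that list.
   - The CEC's listed look at sensor and pump data is optional and worded for device-related events. A separate list says that review of events may call for the upload, without that restriction.
   - Section 11.7 proceeds only for events judged device related.

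7. **What does not use relatedness.** SAP Section 7.9.6 summarises the incidence of severe hyperglycemia without regard to cause, and Protocol Section 12.2 gives the DMC its overall rate. SAP Section 7.9.1 judges success on HbA1c change and time in range.

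**The case against.** The strongest reply is that this is an illustration placed beneath governing text that already gives the right answer. Section 11.6 requires review of the whole event with uploads, excludes a relationship only on stated grounds, addresses false device results and defaults to *Possible*. Row 1 can be read as the case where that review found no device cause. The CEC then checks the classification, and Section 12.1 tells it to weigh device malfunction in severe hyperglycemia.

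Much of this stands. A reader might infer that sensor and algorithm events will be counted as non-device events in the final results. The documents do not support that, because the CEC adjudication is what is analysed.

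It does not remove the point. The lead-in states what code an event would have, and row 1 carries no condition that other device causes have been excluded. A site has to set the example aside in order to follow the definitions. An initial *Not related* code can also reduce later scrutiny, given how the CEC's listed data review is worded.

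A reader might also try to size the problem from Table 5 in Section 12.2: 100 pediatric subjects × 90 / 365.25 days = 24.6 patient-years, and 24.6 × 71.64 / 100 = 17.7 events, of which some share would be miscoded. This does not hold up. The 71.64 rate is for ages under 15, while the cohort is 7–17 and only a minimum of 20 subjects aged 7–13 is specified. No document splits severe hyperglycemia by cause, and the sum ignores CEC correction.

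**Conclusion.** The example is inconsistent with its own section and should be corrected. Taken literally, it leads sites to *Not related* on evidence that argues only against a set fault, contrary to the definition of device, the risks listed in Section 10.1, and the *Not related* and *Possible* definitions.

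The consequence is limited to initial ADE and SADE coding by sites, entry to the Section 11.7 assessment, and the DMC's device-related rate. For that rate, the documents do not say whether site or CEC coding is used. Total severe hyperglycemia incidence and the primary endpoints are unaffected. The number of events at risk cannot be derived from the documents.

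The conclusion assumes that some sites will apply the table as worded. The contradiction in the text does not depend on that assumption.

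**What to change.** Reconcile the example with the definitions above it in Section 11.6:

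- Limit row 1 to events where glucose improved without a set or site change **and** review of the device uploads shows no sensor, pump or SmartGuard contribution around the time of the event. These stay *Not related*.
- Add a row for events that improved without a set or site change where such a contribution, close in time to the event, cannot be ruled out, or where the upload is unavailable. These are coded *Possible* or higher under the existing definitions.

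The link in time matters. Without it, any signal loss or SmartGuard exit on the upload would make an event related, which would go against the section's own warning that wearing the device does not make an event related.

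The cost is two lines in the table and a clarification to sites. No new data are needed, since uploads are already part of the causality review. The downside is a possibly higher device-related AE count.
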